### 11.3 Partial Response

Requires  $> 50\%$  decrease in peripheral lymphocyte count from pre-treatment value,  $> 50\%$  reduction in lymphadenopathy, and/or  $> 50\%$  reduction in Splenomegaly or hepatomegaly for a period of at least two months from completion of therapy. All lymph nodes will be measured bi-dimensionally and the sums of these added to determine if  $50\%$  or greater reduction has occurred. Patients may have bone marrow lymphoid nodules and persistent cytopenias. Additionally, these patients must have one of the following:

- Polymorphonuclear leukocytes  $\geq 1500/\mu\text{L}$  or 50% improvement from pre-treatment value.
- Platelets  $> 100,000/\mu\text{L}$  or 50% improvement from pre-treatment value.
- Hemoglobin  $> 11.0 \text{ g/dL}$  (untransfused) or 50% improvement from pre-treatment value.

## 11.4 Stable Disease

Patients who do not fulfill the criteria for complete or partial response as defined above but do not exhibit progressive disease will be considered as having stable disease.

## 11.5 Progressive Disease

Characterized by any one of the following events:

- $\geq 50\%$  increase in the products of at least two lymph nodes on two consecutive determinations two weeks apart (at least one lymph node must be  $\geq 2 \text{ cm}$ ); appearance of new palpable lymph nodes.
- $\geq 50\%$  increase in the size of the liver and/or spleen as determined by measurement below the respective costal margin; appearance of palpable hepatomegaly or splenomegaly, which was not previously present.
- $\geq 50\%$  increase in the absolute number of circulating lymphocytes to at least  $5,000/\mu\text{L}$ .
- Transformation to a more aggressive histology (i.e. Richter's syndrome or prolymphocytic leukemia with  $> 55\%$  prolymphocytes).
- Patients not fulfilling the above criteria for progressive disease but demonstrating a decrease in hemoglobin  $> 2 \text{ g/dL}$  or a decrease  $\geq 50\%$  in platelet or granulocyte count, will not be rated as progressive disease because these may occur as both a consequence of therapy and of underlying CLL. A bone marrow biopsy in such settings is strongly encouraged.

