**Table 2: Lenalidomide Dosing and Administration**

Treatment Arm	Cycle	Dose	Ancillary Medications	Schedule	Cycle Length
A Concurrent	1	2.5 mg/day	Allopurinol 300 mg/day beginning 3 days prior to lenalidomide and continuing through at least the end of Cycle 1	Days 1-28 continuous	28 days
	2+	5 mg/day	Dexamethasone may be given for up to 7 days during Cycles 1 and 2 for symptomatic tumor flare		

B Sequential	1-3	No lenalidomide	Allopurinol 300 mg/day beginning 3 days prior to lenalidomide and continuing through at least the end of Cycle 4  Dexamethasone may be given for up to 7 days during Cycles 4 and 5 for symptomatic tumor flare	Days 1-28 continuous	
	4	2.5 mg/day			
	5+	5 mg/day			

Lenalidomide dosing and administration are summarized in **Table 2**. Lenalidomide treatment will be administered at 2.5 mg/day during the first cycle of treatment (Arm A: Cycle 1; Arm B: Cycle 4) to minimize risks for tumor flare and/or tumor lysis. The dose of lenalidomide will be increased to 5 mg/day beginning as early as the second cycle of therapy (Arm A: Cycle 2; Arm B: Cycle 5) if all of the following criteria are met on Day 1:

- No clinically significant Grade 3 or greater non-hematologic toxicities attributable to lenalidomide during the preceding cycle.
- Any hematologic toxicity is resolved to  $\leq$  Grade 1.
- Maintained platelet count  $>50K$  at all times during the previous cycle.
- Maintained ANC  $>1K$  at all times during the preceding cycle.
- Any other drug-related adverse events have resolved to Grade  $\leq 1$  severity.

During the first cycle of lenalidomide exposure, and any cycle in which the dose is subsequently escalated, patients are seen on Days 1 and 8 for laboratory evaluation (CBC, chemistries), history, and physical examination to evaluate for tumor lysis and/or tumor flare, respectively. Management of tumor flare response is detailed in **5.2.1** below.

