Patients not meeting criteria for dose escalation upon beginning the second cycle of lenalidomide can be re-evaluated for dose escalation at the start of subsequent cycles, at which time the same criteria will apply. However, dose escalation beyond 5 mg/day will not be permitted so as to limit the risk in this patient population who would not otherwise be receiving therapy. Criteria for removal from study ([Section 5.5](#)), dose modifications for toxicity ([Section 6.1](#)), and guidelines for intrasubject dose escalation ([Section 6.4](#)) are further discussed below. Management of biochemical and clinical tumor lysis is described in **6.3.9** and **6.3.10** below.

Lenalidomide can be taken without regard to meals. If a patient misses a dose of lenalidomide, the patient should take it as soon as he or she remembers that day. If the patient does not remember until the next day, the patient should skip the missed dose. Patients should NOT take two doses the same day. Missed doses will not be made-up, and the resulting remainder of study drug should be returned with the bottle at the next follow-up visit.

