## 5.2 General Concomitant Medication and Supportive Care Guidelines

Patients should receive full supportive care, including transfusions of blood and blood products, antibiotics, and antiemetics when appropriate. All concomitant medications, including the reason(s) for treatment, dosage, and the dates of treatment, should be recorded on the flow sheets.

5.2.1 **Corticosteroids for tumor flare:** Swelling, erythema, and tenderness of lymph nodes (especially pathologically involved lymph nodes), with/without fever and rash, are expected effects of treatment with lenalidomide. First line treatment is analgesics (e.g. NSAIDs, acetaminophen, oral narcotics) or corticosteroids at the discretion of the treating physician. If the treating physician believes steroids are indicated, administration of dexamethasone (recommended dose = 4mg/day x 7 days) during the first two cycles of lenalidomide treatment is permitted. Steroid administration beyond 7 days can be considered after consultation with the principal investigator.

5.2.2 **Allopurinol:** All patients, unless allergic, should receive allopurinol 300 mg orally daily starting 3 days prior to initiating lenalidomide therapy and continuing through at least the end of the first cycle of treatment as tumor lysis syndrome prophylaxis. This coincides with Cycle 1 in Arm A and Cycle 4 in Arm B. Allopurinol may be continued through the second cycle of lenalidomide treatment and beyond at the discretion of the treating physician. If the patient is allergic to allopurinol, this drug will be omitted.

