### 6.3.8 Tumor Flare

- Swelling, erythema, and tenderness of lymph nodes (especially pathologically involved lymph nodes) are expected effects of treatment with lenalidomide. First line treatment is analgesics (e.g. NSAIDs, acetaminophen, oral narcotics) or corticosteroid therapy at the discretion of the treating physician. Suggested corticosteroid dosing is detailed in **5.2.1** above.
- Symptomatic tumor flare alone will not require that lenalidomide be held unless:
  - Symptomatic tumor flare persists beyond 3 days of corticosteroid treatment
  - Treating physician believes it is in the patient's best interest.
- If lenalidomide is held, therapy should be resumed when tumor flare resolves, or at the principal investigator's discretion.

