### Schedule of Study Assessments: Arm B (Sequential)

Procedure	Screening	Cycle 1	Cycle 2	Cycle 3	Cycle 4 & 5				Cycle 6	Cycle 7+	End of Therapy o	Follow-Up p
					W1	W2	W3	W4				
Clinical Assessment												
Informed Consent	X											
Physical Examination a	X	X	X	X	X	X	X	X	X	X	X	
ECOG Performance Status b	X	X	X	X	X	X	X	X	X	X	X	
Concomitant medications	X	X	X	X	X	X	X	X	X	X	X	
Interval infection history c		X	X	X	X	X	X	X	X	X	X	
Record adverse events		X	X	X	X	X	X	X	X	X	X	
Perform Drug Accountability d	X				X	X	X	X	X	X	X	
Education and Counseling e					X				X	X	X	
Response assessment n					C5					X n	X	X
Laboaratory Studies and Procedures												
ECG	X											
Complete blood count m	X	X	X	X	X	X	X	X	X	X	X	X
Serum chemistries f	X	X	X	X	X	X	X	X	X	X	X	
Urinalysis	X											
Quantitative immunoglobulins	X	X		X	X					Every 6 mo	X g	X
Direct and indirect antiglobulin test	X											
TSH	X										X	
Pregnancy testing g	X				X g	X	X	X	X	X	X	
Bone marrow biopsy h	Optional										X	
Risk stratification studies i	X											
CT scans r	X										X	
Anti-pneumococcal antibody titers		X		X	X							
Treatment												
Allopurinol l					X	X	X	X				
Thromboprophylaxis k					X	X	X	X	X	X		
Dispense Lenalidomide l					X	X	X	X	X	X		
Lenalidomide					X	X	X	X	X	X		
PCV13 administration		X		X								
Correlative Studies												
Pharmacokinetic Studies s					C5 D1,2							
Pharmacodynamic Studies t	X	X			C4 D1,3 C5 D1	C4 D8			X			

- a. Physical examination should include vitals signs, weight, general physical examination (including neurologic examination), measurement of liver and spleen span in centimeters below the costal margin in the anterior axillary line, and bi-dimensional measurement of cervical, supraclavicular, axillary, and inguinal nodes.
- b. See [Appendix A](#).
- c. See [6.3.10](#) for required information to be documented for each episode of infection.
- d. Patient medication diary is reviewed to assess patient compliance on the first day of each cycle in which lenalidomide is administered.

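### Section 11.5 scores a newly palpable lymph node as progression on one examination, with no rule for lenalidomide tumour flare: a narrow gap that touches descriptive outputs only

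*Combined protocol and SAP*

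**What the plan says.** Section 11.5 lists several events, any one of which is PD. Its nodal item has two parts. An increase of at least 50% in existing nodes must be found on two consecutive determinations two weeks apart. The second part, "appearance of new palpable lymph nodes", follows a semicolon and carries no repeat examination and no size threshold. The section makes one allowance for drug effect: falls in haemoglobin, platelets or granulocytes "will not be rated as progressive disease because these may occur as both a consequence of therapy and of underlying CLL".

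Flare is handled elsewhere, as a matter of patient management. Section 6.3.8 states: "Swelling, erythema, and tenderness of lymph nodes (especially pathologically involved lymph nodes) are expected effects of treatment with lenalidomide". Section 5.2.1 says the same of nodal swelling, "with/without fever and rash, are expected effects of treatment with lenalidomide". Section 6.3.8 normally continues the drug: "Symptomatic tumor flare alone will not require that lenalidomide be held unless" the flare outlasts three days of corticosteroid or the treating physician judges a hold to be best.

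On timing, footnote a of the study calendar (Section 10) makes "bi-dimensional measurement of cervical, supraclavicular, axillary, and inguinal nodes" part of each physical examination. Footnote n starts response assessment at Cycle 3 in Arm A and Cycle 5 in Arm B, then every two cycles of lenalidomide.

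**The concern.** The plan recognises that a drug effect can look like progression, but writes the exemption for blood counts only. A node that swells through flare can be managed under Section 6.3.8 as an expected drug effect and, under the literal wording of Section 11.5, be scored as PD from the same examination. I found nothing in Sections 11 or 13 that says how flare is to be scored.

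At stake are the outputs that use Section 11.5:

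- PFS (Section 11.7; a secondary aim in the Schema)
- the two-year progression-free proportion in each arm (Section 13.5)
- duration of response and of stable disease (Section 11.6)
- the response category (Section 13.6.2), where PD is a treatment failure. The documents do not say whether an early PD or a later response sets a patient's single category.

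**Working it through.** The plan gives no figure to reproduce here. The check is a comparison of texts, followed by simple arithmetic on size.

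**1. The rules in Section 11.5 side by side**

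| Finding | Repeat determination | Exempt as therapy effect |
|---|---|---|
| Growth of existing nodes | Yes, two weeks apart | No |
| New palpable node | No | No |
| Fall in haemoglobin, platelets or granulocytes | Not applicable | Yes |

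Only the new-node row has neither protection.

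**2. Whether a scored assessment can fall in the flare period.** Completed lenalidomide cycles at the first response assessment, taking it at the start of the cycle (the calendar gives no day):

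- Arm A: drug from Cycle 1, assessment at Cycle 3, so 3 − 1 = 2 cycles.
- Arm B: drug from Cycle 4, assessment at Cycle 5, so 5 − 4 = 1 cycle.

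Table 2 allows dexamethasone for flare in Cycles 1 and 2 (Arm A) and Cycles 4 and 5 (Arm B). Arm B's first assessment is therefore inside that window, and Arm A's comes just after it.

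Later exposure is also possible. A patient not escalated at the second lenalidomide cycle "can be re-evaluated for dose escalation at the start of subsequent cycles", and Section 6.4 permits re-escalation after a reduction. In "any cycle in which the dose is subsequently escalated, patients are seen on Days 1 and 8", partly to look for flare. Nothing expressly bars recording PD at a visit before the footnote n schedule begins.

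**3. What one misclassified patient does.** If the patient would otherwise be progression-free at two years, the arm's proportion falls by 1/22 = 4.5 points (22 evaluable patients) or 1/24 = 4.2 points (24 enrolled).

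**4. Illustrative range.** Let s be the true two-year progression-free share and f the share of those patients whose flare is scored as PD. The observed share is s × (1 − f), and the expected number misclassified among 44 is 44 × s × f. The documents give neither input, so all values below are assumptions.

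| f | s = 0.60: observed (patients) | s = 0.80: observed (patients) |
|---|---|---|
| 2% | 58.8% (0.5) | 78.4% (0.7) |
| 5% | 57.0% (1.3) | 76.0% (1.8) |
| 10% | 54.0% (2.6) | 72.0% (3.5) |
| 20% | 48.0% (5.3) | 64.0% (7.0) |

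**5. Why no row can be chosen.** The only flare frequency is the adverse event table in Section 7.1, which places tumour flare in the column for events below 3%. Applied here, that would be under 0.03 × 22 = 0.66 flares per arm. The table pools 4081 patients and is not specific to CLL, and its own footnote warns of serious flare in CLL. Section 2.2.1 reports more flare than expected at 10 to 25 mg/day in refractory disease but gives no rate. The share of flares that make a node newly palpable is not stated.

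**The case against.** The strongest reply is that the route is narrow and little depends on it.

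- **Visits.** Early visits exist partly to detect flare. The calendar marks no response assessment in Arm A's first two cycles, so most early flare there would be seen before response is scored. This stands as a limit. A reader might infer that every weekly examination marked in the first two lenalidomide cycles is a scoring visit; footnote n does not support that, and Section 5.1.1 describes Days 1 and 8 rather than weekly visits. The limit is incomplete, given Arm B's Cycle 5 assessment and later escalations.
- **Recognition.** Flare is tender, red swelling, mainly of nodes already involved, and growth of known nodes has the two-determination rule. An investigator who recognises flare may well not record PD. That is plausible, but it leaves the scoring to unwritten judgement.
- **Guideline.** Section 11.1 cites the 2008 IWCLL criteria. Whether those deal with flare cannot be checked here. The section applies them as set out in the text that follows, so Section 11.5 is the operative rule.
- **Importance.** PFS is absent from the objectives in Section 1.2, and Section 13.5 plans no formal arm comparison of time-to-event outcomes. This stands, and it sets the severity.
- **Timing.** Section 9 says the study endpoints have been met, so a change now is made after the fact. This also stands, and it argues for a sensitivity analysis rather than a silent rescoring.

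**Conclusion.** The gap is real and minor. Followed literally, Section 11.5 counts a transient flare as PD when it makes a node newly palpable at a scored assessment. The effect is confined to descriptive outputs. Its size is unknown: 4.2 to 4.5 points on an arm's two-year proportion for each affected patient who would otherwise be progression-free, with an unknown number affected, possibly none.

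Three stronger conclusions that a reader might draw are not supported.

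- **That it threatens the trial's decisions.** The antibody endpoint does not use Section 11.5. The CR rule in Section 13.3 counts a CR on two consecutive evaluations within two years, which an early PD does not by itself remove. Time to first treatment and mandatory withdrawal (Section 5.3) rest on IWCLL criteria.
- **That it biases the arms.** The first assessment falls after two lenalidomide cycles in Arm A and one in Arm B. The documents give no flare rate by cycle and do not confine PD to those assessments, so no direction or size can be claimed.
- **That the figure below 3% caps the problem.** It is a pooled frequency from other settings, not a ceiling for CLL at this dose.

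**What to change.** Add to Section 11.5 wording such as: *New palpable lymph nodes reported as a tumour flare adverse event during the first two cycles of lenalidomide, or during any cycle in which the dose is escalated, are PD only if still present at a second scheduled examination at least two weeks later. If so, PD is dated to the first observation. The same rule applies in both arms.* Leave the rule for enlarged nodes and the transformation criterion unchanged.

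The two-week interval is the one Section 11.5 already uses for existing nodes. The rule is tied to the adverse event report because Section 6.3.8 requires no flare record of its own, whereas Section 7.4 requires all adverse events to be reported.

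For data already recorded, apply the rule to the node measurements and adverse events as a sensitivity analysis. State that it was added late, and give the number of patients reclassified in each arm, including zero.

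The cost is a few lines of text and no new visits. With Day 1 and Day 8 visits in 28-day cycles, a node first seen on Day 1 is rechecked by the next Day 1, 29 − 1 = 28 days later, and one first seen on Day 8 after 29 − 8 = 21 days. The worst case with Day 1 visits only is an unscheduled finding on Day 16. The next Day 1 is 13 days away, so the recheck falls 57 − 16 = 41 days after the finding, before visit windows. The downsides are somewhat later confirmation of a true early nodal progression, which keeps its original date, and disclosure of a late change.

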## 11.6 Duration of response

### 11.6.1 Duration of overall response

The duration of overall response is measured from the time measurement criteria are met for CR or PR (whichever is first recorded) until the first date that recurrent or progressive disease is objectively documented (taking as reference for progressive disease that smallest measurements recorded since treatment started).

The duration of overall CR is measured from the time measurement criteria are first met for CR until the first date that recurrent disease is objectively documented.

#### **11.6.2 Duration of stable disease**

Stable disease is measured from the start of the treatment until the criteria for progression are met, taking as reference the smallest measurements recorded since treatment started.

#### **11.7 Progression Free Survival (PFS)**

PFS is defined as the duration of time from start of treatment to time of disease progression or death secondary to any cause.

### **12. DATA REPORTING / REGULATORY REQUIREMENTS**

Adverse event lists, guidelines, and instructions for AE reporting can be found in [Section 7.0](#) (Adverse Events: List and Reporting Requirements).

#### **12.1 Data Reporting**

##### **12.1.1 Method**

This study will be monitored by the Clinical Data Update System (CDUS) version 3.0. Cumulative CDUS data will be submitted quarterly to CTEP by electronic means. Reports are due January 31, April 30, July 31, and October 31. Instructions for submitting data using the CDUS can be found on the CTEP Web site ([http://ctep.cancer.gov/protocolDevelopment/electronic\\_applications/cdus.htm](http://ctep.cancer.gov/protocolDevelopment/electronic_applications/cdus.htm)). **Note:** All adverse events that have occurred on the study, including those reported through CTEP-AERS, must be reported via CDUS.

##### **12.1.2 Responsibility for Data Submission**

N/A

#### **12.2 CTEP Multicenter Guidelines**

N/A

#### **12.3 Collaborative Agreements Language**

The agent(s) supplied by CTEP, DCTD, NCI used in this protocol is/are provided to the NCI under a Collaborative Agreement (CRADA, Agent-CRADA, CTA, CSA) between the Pharmaceutical Company(ies) (hereinafter referred to as “Collaborator(s)”) and the NCI Division of Cancer Treatment and Diagnosis. Therefore, the following

obligations/guidelines, in addition to the provisions in the “Intellectual Property Option to Collaborator” (<http://ctep.cancer.gov/industry>) contained within the terms of award, apply to the use of the Agent(s) in this study:

1. Agent(s) may not be used for any purpose outside the scope of this protocol, nor can Agent(s) be transferred or licensed to any party not participating in the clinical study. Collaborator(s) data for Agent(s) are confidential and proprietary to Collaborator(s) and shall be maintained as such by the investigators. The protocol documents for studies utilizing investigational Agents contain confidential information and should not be shared or distributed without the permission of the NCI. If a copy of this protocol is requested by a patient or patient’s family member participating on the study, the individual should sign a confidentiality agreement. A suitable model agreement can be downloaded from: <http://ctep.cancer.gov>.
2. For a clinical protocol where there is an investigational Agent used in combination with (an)other investigational Agent(s), each the subject of different collaborative agreements , the access to and use of data by each Collaborator shall be as follows (data pertaining to such combination use shall hereinafter be referred to as “Multi-Party Data”). :
  - a. NCI will provide all Collaborators with prior written notice regarding the existence and nature of any agreements governing their collaboration with NIH, the design of the proposed combination protocol, and the existence of any obligations that would tend to restrict NCI's participation in the proposed combination protocol.
  - b. Each Collaborator shall agree to permit use of the Multi-Party Data from the clinical trial by any other Collaborator solely to the extent necessary to allow said other Collaborator to develop, obtain regulatory approval or commercialize its own investigational Agent.
  - c. Any Collaborator having the right to use the Multi-Party Data from these trials must agree in writing prior to the commencement of the trials that it will use the Multi-Party Data solely for development, regulatory approval, and commercialization of its own investigational Agent.
3. Clinical Trial Data and Results and Raw Data developed under a Collaborative Agreement will be made available exclusively to Collaborator(s), the NCI, and the FDA, as appropriate and unless additional disclosure is required by law or court order as described in the IP Option to Collaborator ([http://ctep.cancer.gov/industryCollaborations2/intellectual\\_property.htm](http://ctep.cancer.gov/industryCollaborations2/intellectual_property.htm)). Additionally, all Clinical Data and Results and Raw Data will be collected, used, and disclosed consistent with all applicable federal statutes and regulations for the protection of human subjects including, if applicable, the *Standards for Privacy of Individually Identifiable Health Information* set forth in 45 CFR Part 164.
4. When a Collaborator wishes to initiate a data request, the request should first be sent to the NCI, who will then notify the appropriate investigators (Group Chair for

Cooperative Group studies, or PI for other studies) of Collaborator's wish to contact them.

5. Any data provided to Collaborator(s) for Phase 3 studies must be in accordance with the guidelines and policies of the responsible Data Monitoring Committee (DMC), if there is a DMC for this clinical trial.
6. Any manuscripts reporting the results of this clinical trial must be provided to CTEP by the Group office for Cooperative Group studies or by the principal investigator for non-Cooperative Group studies for immediate delivery to Collaborator(s) for advisory review and comment prior to submission for publication. Collaborator(s) will have 30 days from the date of receipt for review. Collaborator shall have the right to request that publication be delayed for up to an additional 30 days in order to ensure that Collaborator's confidential and proprietary data, in addition to Collaborator(s)'s intellectual property rights, are protected. Copies of abstracts must be provided to CTEP for forwarding to Collaborator(s) for courtesy review as soon as possible and preferably at least three (3) days prior to submission, but in any case, prior to presentation at the meeting or publication in the proceedings. Press releases and other media presentations must also be forwarded to CTEP prior to release. Copies of any manuscript, abstract and/or press release/ media presentation should be sent to:

Regulatory Affairs Branch, CTEP, DCTD, NCI  
[name]  
[name]  
[contact]  
Email: [[contact]](mailto:[contact])

The Regulatory Affairs Branch will then distribute them to Collaborator(s). No publication, manuscript or other form of public disclosure shall contain any of Collaborator's confidential/ proprietary information.

